### 8.2.3 Analysis of Secondary Efficacy Variables

The secondary efficacy endpoints of TTNT, DMFS, ORR and QoL using the EQ-5D-5L or EQ-5D-Y will be compared between treatment arms.

The secondary efficacy endpoints will only be evaluated if at least one of the primary efficacy endpoints (PFS/OS) demonstrates superiority for CMB305 over placebo. Furthermore, to control the overall family-wise type I error rate at 1-sided  $\alpha = 0.025$  for the secondary efficacy endpoints, the secondary efficacy endpoint of TTNT will be tested first at 1-sided alpha of 0.025. DMFS will be tested at 1-sided alpha of 0.025 only if TTNT shows significant improvement.

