7.10 Multiplicity

The study is to be conducted with PFS and OS as 2 primary endpoints with the goal of a regulatory approval based on PFS or OS. The overall type I error probability is specified to be 1-sided 0.025 with success for either of the 2 primary endpoints defining study success using the Bonferroni method to specify that each endpoint will be evaluated using a type I error probability of 1-sided 0.0125 in order to protect the overall type I error.

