## 4 SAMPLE SIZE DETERMINATION

A total of 248 subjects will be randomly assigned in a 1:1 ratio such that 124 subjects will be included in each of the 2 treatment arms. The study is powered at 90% with 179 death events required to detect a HR of 0.59, which corresponds to a 41% reduction in the risk of death, and an approximately 69% increase in median survival compared with a placebo median survival of 20 months, and uses a 1-sided log-rank test, with an alpha of 0.0125, a 1:1 randomization ratio, and an interim OS non-binding futility analysis with boundary of HR = 1.0 at 67% of information time (120 death events from the 179 required death events for the final OS analysis). A total of 248 subjects will yield the 179 events required, under the assumption of 24 months for enrollment (25% of subjects enrolled in the first year and 75% of subjects enrolled in the second year) plus 42 additional months of follow-up.

With 141 PFS events, the study is powered at 90% to detect a HR of 0.55, which corresponds to a 45% reduction in the risk of PFS events (either disease progression or death), and an approximately 82% increase in median PFS compared with a placebo median PFS of 4 months, and uses a 1-sided log-rank test, with an alpha of 0.0125, and a 1:1 randomization ratio.

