### 7.3 Multiplicity

The study is to be conducted with PFS and OS as 2 primary endpoints with the goal of a regulatory approval based on either PFS or OS. The overall type I error probability is specified to be 1-sided 0.025 with success for either of the 2 primary endpoints defining study success using the Bonferroni method to specify that each endpoint will be evaluated using a type I error probability of 1-sided 0.0125 in order to protect the overall type I error. In case both final PFS analysis and final OS analysis have 1-sided  $0.0125 \leq p < 0.025$ , or one of the analyses has 1-sided  $0.0125 \leq p < 0.025$  while the other has 1-sided  $p < 0.0125$ , the overall type I error will be controlled at 1-sided 0.025 with statistical significance applied to both PFS and OS analyses using the Hochberg method.

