## **8.2.2 Analysis of Primary Efficacy Variables**

### **8.2.2.1 Primary Analyses**

The null hypothesis of no difference in PFS/OS between CMB305 and placebo, in the ITT set, will be tested using a stratified log-rank test stratified by randomized stratification factors: disease status at screening (locally advanced unresectable versus metastatic), tumor response during screening (PR/SD versus CR/NED), and by baseline presence of anti-NY-ESO-1 antibody (yes versus no)).

The null hypothesis will be rejected and it will be concluded that PFS/OS on CMB305 is superior to that on placebo if the 1-sided p value at the final analysis for the stratified log-rank test is less than the pre-specified alpha as discussed in Multiplicity Section. Success for either of the 2 primary endpoints defines study success.

The Kaplan-Meier curve will summarize PFS/OS graphically by treatment arm. Tabular summaries of the Kaplan-Meier curves, including the median and 2-side 97.5% and 95% CI will be provided by treatment arm. The 4, 6, 8, and 10 month PFS rate and 12, 18, 24, and 30 month OS rate will be provided by treatment arm.

The associated HR and its 2-sided 97.5% and 95% CI will be provided using the stratified Cox proportional hazard model for PFS/OS, comparing treatment arm, stratified by the randomized stratification factors .

The final PFS analysis will be conducted when a total of 141 PFS events occur. The final OS analysis will be conducted when a total of 179 deaths occur.

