## **9 CHANGES FROM THE PROTOCOL SPECIFIED STATISTICAL ANALYSES**

If discrepancies exist between the text of the statistical analysis as planned in the protocol, and the final SAP, a protocol amendment will not be issued and the SAP will prevail.

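### One primary win opens TTNT and DMFS at the full one-sided 0.025, although that win frees at most 0.0125 to pass on

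*SAP*

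**What the plan says.** Protocol 7.10 splits the overall one-sided 0.025 equally: "each endpoint will be evaluated using a type I error probability of 1-sided 0.0125 in order to protect the overall type I error". Success on PFS or OS alone is study success. SAP 7.3 repeats this split and adds a step that the protocol lacks. If both p-values are below 0.025, both endpoints are declared, "with statistical significance applied to both PFS and OS analyses using the Hochberg method". Where the documents differ, SAP section 9 says that "a protocol amendment will not be issued and the SAP will prevail".

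For the secondaries, SAP 8.2.3 and Protocol 7.7.2 give the same rule. In the SAP's words, the secondaries "will only be evaluated if at least one of the primary efficacy endpoints (PFS/OS) demonstrates superiority". Once they are open, "the secondary efficacy endpoint of TTNT will be tested first at 1-sided alpha of 0.025", and DMFS follows at 0.025 if TTNT is significant. The purpose given is "to control the overall family-wise type I error rate at 1-sided" 0.025 for the secondary endpoints. The level does not depend on whether one or both primaries were rejected.

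On timing, SAP 8.2.2.1 says "The final PFS analysis will be conducted when a total of 141 PFS events occur", and final OS comes at 179 deaths. Neither document says at which of these TTNT and DMFS are tested.

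**The concern.** A gatekeeping scheme can pass on only the alpha that the gate has freed. After a single Bonferroni win that is 0.0125, because the other 0.0125 still belongs to the unrejected primary. Under Hochberg, one clear win lets the second primary be claimed at 0.025, so nothing is left. The plan then spends the same 0.025 on both the second primary and TTNT.

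After a single primary win, two kinds of secondary claim therefore lack study-wide control at 0.025:

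- under Bonferroni primaries, a TTNT or DMFS claim with p between 0.0125 and 0.025;
- under the SAP's Hochberg rule, any TTNT or DMFS claim.

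The unnamed cutoff adds a second gap. The wording does not rule out testing TTNT after PFS and again after OS.

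**Working it through.** **The plan's own figures.** Schoenfeld's formula is d = 4(z₁₋α + z₁₋β)² / (ln HR)², with α = 0.0125 one-sided and 90% power (SAP section 4).

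- The numerator is 4 × (2.2414 + 1.2816)² = 49.65.
- OS: 49.65 / (ln 0.59)² gives 179 deaths, as stated.
- PFS: 49.65 / (ln 0.55)² gives 139 events. The plan states 141, which gives 90.5% power.
- With 179 deaths, OS power is 0.9012 at 0.0125 and 0.9418 at 0.025.
- The interim OS look is for futility only and spends no alpha.

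**One primary effective: hand calculation.** Let OS be effective at its design value, with PFS and TTNT null and the three test statistics independent.

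- Bonferroni: P(false PFS claim) + P(no PFS claim, OS wins, TTNT p < 0.025) = 0.0125 + 0.9875 × 0.9012 × 0.025 = **0.0347**.
- SAP Hochberg: the chance of a false PFS claim is 0.0125 + 0.0125 × 0.9418 = 0.0243. A false TTNT claim without a PFS claim adds 0.9012 × 0.975 × 0.025 = 0.0220. The total is **0.0462**.
- If the effective primary always wins, these become 1 − 0.9875 × 0.975 = 0.0372 and 1 − 0.975² = 0.0494. Whatever the correlation, the bounds are 0.0125 + 0.025 = 0.0375 and 0.025 + 0.025 = 0.05.

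**Allowing for correlation.** The documents give no correlations, so a common value was assumed and 4 million trials were simulated per row. The first four rows have OS effective. The last has PFS effective, for which the other rows are nearly identical.

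| Correlation | Protocol rule | SAP rule | Bonferroni fix | Hochberg fix (both must win) |
|---|---|---|---|---|
| 0 | 0.0347 | 0.0462 | 0.0236 | 0.0243 |
| 0.3 | 0.0356 | 0.0470 | 0.0239 | 0.0248 |
| 0.5 | 0.0347 | 0.0454 | 0.0233 | 0.0250 |
| 0.7 | 0.0324 | 0.0418 | 0.0217 | 0.0250 |
| 0.9 | 0.0281 | 0.0352 | 0.0181 | 0.0251 (simulation error) |

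Passing on only 0.0125 while keeping the full Hochberg step is not enough. At correlation 0 it gives 0.0243 + 0.9012 × 0.975 × 0.0125 = 0.0353.

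**PFS and TTNT both effective.** Assume 90% power for each, correlation 0.8 between them, OS and DMFS null, and other correlations of 0 to 0.7. The chance of a false OS or DMFS claim is 0.032 to 0.035 under the protocol and 0.042 to 0.047 under the SAP.

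**Where there is no problem.** With both primaries null the error is at most 0.025. With both effective and TTNT null it is 0.0248 to 0.0250.

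**Timing.** The inputs are exponential times, 124 subjects per arm, accrual over 24 months with "25% of subjects enrolled in the first year and 75% of subjects enrolled in the second year", PFS medians of 4 and 4/0.55 months, and OS medians of 20 and 20/0.59 months. Expected events reach 141 for PFS at month 23.6 and 179 for OS at month 64.1. The latter fits the plan's 24 + 42 = 66 months. The two readouts are thus about 40 months apart.

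As an illustration only, suppose both primaries win and a null TTNT is tested at each readout. The correlation between the two looks is √(d₁/d₂), which is 0.81 for an assumed TTNT median of 4 months and 0.62 for 12 months. Testing at 0.025 twice gives a false claim with probability 0.039 to 0.044. Testing at 0.0125 and then 0.025 gives 0.030 to 0.033. Deaths as competing events are ignored.

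**The case against.** The strongest reply is that no stated promise is broken. The documents claim 0.025 within the secondary family, and the fixed TTNT-then-DMFS order delivers it. The overall 0.025 is tied to the two primaries. This stands: the finding is a gap in study-wide control, and it matters only if TTNT or DMFS is meant to support a confirmatory claim. But the plan assigns these endpoints formal alpha and gates them on the primaries, which implies such a claim.

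A second reply is that an effective PFS with a null TTNT is hardly credible, because Protocol 5.8.2 bars other cancer treatment before progression. This is fair, and it makes OS effective with PFS and TTNT null the more realistic form of the first case. Protocol 1.1.2 expects benefit beyond RECIST progression and emphasises OS, so that form is plausible. If PFS and TTNT are both effective, the false claim falls on OS or DMFS instead, and the error is about as large.

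Third, the reach is narrow. Under Bonferroni, the excess is a false TTNT result with p between 0.0125 and 0.025, which arises in about 0.9875 × 0.9012 × 0.0125 = 1.1% of trials in the OS-effective case. That is right for the protocol's rule but not for the SAP's.

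Fourth, neither document says that TTNT will be tested twice. That is correct. SAP 8.2.1.1 attaches a cutoff to every analysis but names none for these endpoints, so the re-test figures only show why one should be named.

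**Conclusion.** The concern holds. When exactly one primary is truly effective, the chance of a false claim across primaries and secondaries exceeds 0.025. At about 90% power it is 0.028 to 0.036 under the protocol's rule and 0.035 to 0.047 under the SAP's, which governs. The ceilings are 0.0375 and 0.05. These sizes rest on assumed correlations of 0 to 0.9. The excess is largest at low correlations and disappears only as the correlation approaches 1.

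The effect is limited. Claims on PFS and OS stay valid, the error with both primaries null is at most 0.025, and TTNT and DMFS at 0.025 are sound when both primaries are rejected. It should be fixed because the repair is cheap and a choice made after the PFS result would look data-driven.

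**What to change.** State one rule for the primaries in both documents, and set the secondary levels to match.

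- **Bonferroni primaries:** test TTNT then DMFS at one-sided 0.0125 if exactly one primary is rejected, and at 0.025 only if both are.
- **Hochberg primaries:** open TTNT and DMFS for confirmatory testing only when both primaries are rejected.
- **A secondary claim after one win, with a Hochberg-type step:** use a truncated Hochberg with its fraction stated. For example, fraction 0.5 tests the second primary at (0.5 + 0.5/2) × 0.025 = 0.01875 and leaves 0.025 − 0.01875 = 0.00625 for TTNT and DMFS.

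In every case, name a single data cutoff for the confirmatory TTNT and DMFS tests, so that one p-value meets whichever level the primaries have released, or prespecify a group-sequential boundary. Do not test once after PFS and again at a higher level after OS. Settle this before the final PFS analysis.

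**Cost.** The change is wording in SAP 7.3 and 8.2.3 and in Protocol 7.7.2 and 7.10. Because the SAP prevails, the SAP edit alone would govern. Aligning the protocol is cleaner but may need ethics approval under Protocol 8.14. Under the Bonferroni option, after a single win, TTNT power of 80% at 0.025 falls to Φ(1.960 + 0.842 − 2.241) = 71% at 0.0125, and 90% falls to 84%. The Hochberg option gives up any confirmatory secondary claim after a single win. An early cutoff forgoes later events, and a late one delays the claim.

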#### 8.2.3.1 Time to Next Treatment (TTNT)

TTNT will be analyzed using the same methods described for OS/PFS.

In the event that the percent of subjects with competing events such as death, lost to follow-up and withdrawal of consent in either arm exceeds 3%, the cumulative incidence estimates and Gray's test will be the main TTNT comparison between the treatment arms.

Example code for cumulative incidence estimates and Gray's test:

```

data risk;
  Baseline=1;
  trt=1; output;
  trt=2; output;
  format trt trtgroup.;
run;

proc phreg data=adtte (where=(paramcd='TTNT')) plots(overlay=strata)=cif;
  class trt / param=glm order=internal ref=first;
  model aval*Status(0) = trt baseline / eventcode=1;
  hazardratio 'Subdistribution Hazards' Group / diff=pairwise;
  baseline covariates=risk out=_null_ / rowid=trt;
run;

```

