7.7.2.1 Time to Next Treatment

Time to next treatment is defined as the time from randomization to start of post-study treatment anti-cancer therapy. Subjects who do not start post-study treatment anti-cancer therapy will be censored at their last known date of being alive. TTNT will be analyzed using the same methods described for OS/PFS. In the event that the percent of subjects with competing events in either arm exceeds 3%, the cumulative incidence estimates, and Gray's test will be the main TTNT comparison between the treatment arms.

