#### 5.1.2.1 Time to Next Treatment (TTNT)

TTNT is defined as the time from randomization to the start of post-study treatment subsequent intervention:

[TTNT = start date of subsequent intervention – randomization date + 1].

Subsequent intervention includes anticancer therapy, cancer-related surgery and local regional therapy. Subjects who do not start any post-study treatment intervention will be censored at their last known date of being alive (same as OS).

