#### 5.1.2.2 Distant Metastasis-Free Survival (DMFS)

DMFS is defined as the time from randomization to evidence of a new distant metastasis not documented at time of randomization:

[DMFS = a new distant metastasis documented date – randomization date + 1].

Subjects who do not have any new distant metastasis will be censored at their last tumor assessment.

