### **8.2.2.2 Sensitive Analysis of Primary Endpoints (PFS/OS)**

The sensitive analyses of primary endpoints will include:

- OS using the Safety set, according to the treated arm

- PFS by investigator assessment and OS using the EE set
- PFS by investigator assessment in the ITT set, with start of subsequent anti-cancer therapy as a PFS event
- PFS based on the IRC response assessment, if required, for both ITT and EE sets as supportive analysis
- Stratified Cox proportional hazard model for PFS or OS, in ITT set, with additional covariates of number of cycles in first line chemotherapy, and/or type of prior therapy (adjuvant/neoadjuvant chemotherapy and surgery and/or radiotherapy)
- PFS and OS by Fleming-Harrington weighted log-rank test with  $\rho = 0$ ,  $\gamma = 1$ , for adjustment of delayed effects.
- The Fleming-Harrington weight for late effects is defined as below
 
$$W_n(t) = (S_n(t))^{\rho} (1 - S_n(t))^{\gamma}$$
- PFS and OS by piecewise Cox proportional model in presence of non-proportional hazard for time-varying treatment effect:
 
$$h(t | z_i) = h_o(t) \exp(\alpha z_{1i} + \beta_1 z_{2i} 1(t \leq c_i) + \beta_2 z_{2i} 1(c_i < t \leq c_{i+1}) + \beta_3 z_{2i} 1(t > c_{i+1}))$$

Where  $Z_{1i}$  is time-independent covariates such as stratification factors;  $C_i$  and  $C_{i+1}$  are cut points (e.g. 4 and 8 months, respectively) for time period and  $I(\cdot)$  denotes the indicator function.
- PFS and OS not censoring events that occur after the cutoff.
- OS with competing events being taken into consideration. Competing events for death are “definite” lost to follow-up and withdrawal of consent for continued survival assessments. Both of these competing events are subject to revision for an individual subject with the passage of time. The cumulative incidence estimates will be plotted if the percent of subjects with competing events in either arm exceeds 3%.
- PFS with competing events being taken into consideration. Competing events for PFS event are lost to follow-up, withdrawal of consent, start of other anti-cancer therapy, or two or more missing scans prior to a PFS event. The cumulative incidence estimates will be plotted if the percent of subjects with competing events in either arm exceeds 3%.

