### 8.2.3.2 Distant Metastasis-Free Survival (DMFS)

DMFS will be analyzed using the same methods described for OS/PFS. In the event that the percent of subjects with competing events such as death, lost to follow-up and withdrawal of consent in either arm exceeds 3%, the cumulative incidence estimates and Gray's test will be the main DMFS comparison between the treatment arms.

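### The main TTNT and DMFS comparison counts loss to follow-up and withdrawal of consent as competing events, which favours the arm that loses more subjects

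*SAP*

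**What the plan says.** The endpoint definitions censor anyone without the event. In SAP 5.1.2.1, subjects with no post-study intervention "will be censored at their last known date of being alive". In SAP 5.1.2.2, "Subjects who do not have any new distant metastasis will be censored at their last tumor assessment".

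The analysis sections then introduce a switch. TTNT and DMFS are analysed like OS/PFS, that is by stratified log-rank test, until a threshold is crossed: once the share having "competing events such as death, lost to follow-up and withdrawal of consent in either arm exceeds 3%, the cumulative incidence estimates", together with Gray's test, take over as the main comparison (SAP 8.2.3.1). SAP 8.2.3.2 has the same list and trigger for DMFS.

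Protocol 7.7.2.1 and 7.7.2.2 carry the 3% switch ("In the event that the percent of subjects with competing events in either arm exceeds 3" per cent) but do not say what a competing event is. The list therefore comes from the SAP, and SAP section 9 gives the SAP precedence.

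These are formal tests. Under SAP 8.2.3, once a primary endpoint has succeeded, "the secondary efficacy endpoint of TTNT will be tested first at 1-sided alpha of 0.025", and DMFS follows at the same level only if TTNT is significant.

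SAP 8.2.2.2 uses similar lists in sensitivity analyses of OS and PFS, but only to plot cumulative incidence.

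**The concern.** A competing event makes the event of interest impossible. Death does that. A subject who is lost or withdraws can still start another therapy or develop a metastasis; the trial just does not see it. That is censoring. For OS the SAP itself notes of loss and withdrawal that "Both of these competing events are subject to revision for an individual subject with the passage of time". The remark concerns updating of status, but it fits poorly with treating them as terminal states.

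Gray's test compares cumulative incidence. A subject with a competing event is kept in the risk set as someone who will never have the event. If dropouts are coded this way, each one lowers that arm's cumulative incidence of next treatment or metastasis. Unequal dropout then produces a difference between arms with no treatment effect, in favour of the arm that loses more subjects. TTNT is the gate to DMFS, so the familywise control claimed in SAP 8.2.3 would not be assured. Equal dropout dilutes a real effect.

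**Working it through.** **Inputs from the documents.** 124 subjects per arm; accrual over 24 months, 25% in year 1 and 75% in year 2, plus 42 months of follow-up (SAP 4); 1-sided 0.025 for TTNT (SAP 8.2.3).

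**The plan's own figures.** Schoenfeld events = 4(z₀.₉₈₇₅ + z₀.₉₀)² / (ln HR)², with 4(2.241 + 1.282)² ≈ 49.65:
- OS, HR 0.59: 49.65/0.2784 = 178.3, so 179, as stated.
- PFS, HR 0.55: 49.65/0.3574 = 138.9, so 139, against 141 stated.

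No power or event count is given for TTNT or DMFS.

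**The trigger.** 3% of 124 is 3.72, so 4 subjects in one arm suffice. The chance that deaths alone trigger it is 1 − [P(X ≤ 3)]² with X ~ Bin(124, p): 0.98, 0.42 and 0.07 for p = 5%, 2% and 1%. Dropouts add to the count.

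**The mechanism.** Gray's statistic uses the adjusted risk set Y(t)·(1 − F(t))/S(t) in each arm, where Y is the number at risk, F the cumulative incidence of the event and S the probability of being free of any event type. Coding losses as competing lowers S and keeps the lost subjects in the risk set.

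Example with no true effect: TTNT median 4 months, median time to death before next treatment 40 months, loss 5% on placebo and 15% on CMB305. By month 66 nearly every subject has had the event, died or been lost, so F is 1 − loss − death:
- Placebo: 1 − 0.050 − 0.086 = 0.864.
- CMB305: 1 − 0.150 − 0.077 = 0.773.

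The simulated apparent HR is 0.83. With losses censored, both arms estimate (1/4)/(1/4 + 1/40) = 0.909 and the simulated HR is 1.00.

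**Type I error by simulation.** Assumptions not in the documents: exponential times, about 5% dying before the event, TTNT median 4, 6 or 12 months, non-informative loss in three patterns (exponential with the share eventually lost; exponential with the share lost by the cut-off; uniform over the first 6 months). Tests were unstratified, both as Gray's statistic and as the subdistribution-hazard score, with 3,000–10,000 trials per scenario. The SAP does not say when TTNT is tested, so two cut-offs were used: months 24–26 (141 PFS events fall at about month 23.6 under the plan's assumptions) and month 66 (24 + 42).

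| Loss, placebo vs CMB305 | Dropouts competing, months 24–26 | Dropouts competing, month 66 |
|---|---|---|
| 5% vs 10% | 0.028–0.072 | 0.084–0.136 |
| 5% vs 15% | 0.037–0.152 | 0.22–0.38 |
| 10% vs 5% | 0.005–0.019 | 0.003–0.006 |

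Equal loss gives 0.018–0.032. With only death competing and dropouts censored, the rate is 0.019–0.032 throughout.

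A second set at month 66, with 9–23% dying first and medians 4, 8 and 12 months, gave 0.070–0.098 for 5% vs 10% and 0.15–0.26 for 5% vs 15%, against 0.021–0.030 with dropouts censored.

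**Power (1-sided 0.025).**

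| Scenario | Cut-off | Dropouts competing | Dropouts censored, death competing |
|---|---|---|---|
| HR 0.55, median 4, loss 10% vs 5% | 24–26 | 0.72–0.83 | 0.90–0.95 |
| same | 66 | 0.46–0.66 | 0.92–0.97 |
| HR 0.55, median 4, loss 10% vs 10% | 24–26 | 0.82–0.89 | 0.90–0.95 |
| same | 66 | 0.68–0.80 | 0.93–0.97 |
| HR 0.70, median 6, loss 10% vs 10% (second set) | 66 | 0.32 | 0.51 |

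**The case against.** - **Coding is not explicit.** SAP 8.2.3.1 and 8.2.3.2 list events that set off the switch. They do not say in so many words how a lost subject enters Gray's test, and the example code shows only a censoring code and an event code. This is true, but naming loss and withdrawal as competing events makes competing coding the natural reading. If censoring is meant, the SAP contradicts itself and still needs correcting.
- **Unequal dropout is not expected.** The trial is double-blind with matched placebos, and follow-up continues after treatment stops. Nothing in the documents suggests different loss by arm, and 5% vs 15% has no documentary basis. This limits the likely size of the bias, not its direction, and does not remove the power loss under equal dropout.
- **Month 66 may not apply.** If PFS succeeds, TTNT could be tested near month 24, where inflation is much smaller. This stands, so the months 24–26 figures should be read first.
- **Consequences are limited.** Harm needs a primary success, a triggered switch and unequal loss. This stands.
- **Censoring is not perfect either.** Loss related to prognosis would bias the censored analysis too. That calls for sensitivity analyses, not for counting dropouts as event-free.

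**Conclusion.** The concern holds. The named competing events include two that are not competing events, the rule governs the main test of the first two secondary endpoints, and it conflicts with the SAP's own endpoint definitions.

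The direction is certain: the arm with more loss is favoured. The size is not, because it rests on assumed dropout, death and event rates. A 5-point excess of loss on CMB305 takes the nominal 0.025 to roughly 0.03–0.07 near month 24 and 0.07–0.14 at month 66. A 10-point excess gives about 0.04–0.15 and 0.15–0.38, the top of that range coming from the least favourable assumptions. Reversed imbalance makes the test conservative; equal loss leaves type I error near nominal but lowers power. DMFS was not simulated separately, but the mechanism is the same. PFS and OS conclusions are untouched. This should be fixed before unblinding, but it does not threaten the trial's primary result.

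**What to change.** 1. In SAP 8.2.3.1 and 8.2.3.2, name death without the event as the only competing event, for both the 3% count and the test. State that lost and withdrawn subjects are censored, at last known alive date for TTNT and last tumor assessment for DMFS.
2. Amend SAP 5.1.2.1 and 5.1.2.2 to match. They currently censor every subject without the event, including those who die, so they need to say that death is treated as competing when Gray's test applies.
3. Specify Gray's test stratified by the three randomisation factors, with status codes for event, death and censoring. The present example fits an unstratified subdistribution-hazard model, and its hazard-ratio statement names a variable, Group, that is not in the model.
4. In SAP 8.2.2.2, delete the OS competing-event bullet and stop listing loss, withdrawal and missed scans as competing events for PFS. This is minor, because both bullets only produce plots.

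The 3% switch would still choose the main test from post-randomisation counts; fixing one test in advance would be cleaner.

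The cost is SAP wording and programming, with no extra data. Gray's test with death competing still has less power than a log-rank test that censors deaths. At HR 0.68, median 6 months and 10% vs 5% loss, it is 0.51–0.59 against 0.53–0.61 at months 24–26, and 0.62–0.70 against 0.79–0.80 at month 66. The sponsor should accept that knowingly.
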